## Annex 10 ENCePP Checklist for study protocols

Section 1: Milestones	Yes	No	N/A	Page Number(s)
1.1 Does the protocol specify timelines for				
1.1.1 Start of data collection 				14
1.1.2 End of data collection 				14
1.1.3 Study progress report(s)				14
1.1.4 Interim progress report(s)				14
1.1.5 Registration in the EU PAS register				
1.1.6 Final report of study results.				14

Comments:

 Date from which information on the first study is first recorded in the study dataset or, in the case of secondary use of data, the date from which data extraction starts.

 Date from which the analytical dataset is completely available.

Section 2: Research question	Yes	No	N/A	Page Number(s)
2.1 Does the formulation of the research question and objectives clearly explain:				
2.1.1 Why the study is conducted? (e.g. to address an important public health concern, a risk identified in the risk management plan, an emerging safety issue)				17
2.1.2 The objective(s) of the study?				17
2.1.3 The target population? (i.e. population or subgroup to whom the study results are intended to be generalised)				17
2.1.4 Which formal hypothesis (-es) is (are) to be tested?				
2.1.5 If applicable, that there is no a priori hypothesis?				

Comments:

Section 3: Study design	Yes	No	N/A	Page Number(s)
3.1 Is the study design described? (e.g. cohort, case-control, randomised controlled trial, new or alternative design)				18-20
3.2 Does the protocol specify the primary and secondary (if applicable) endpoint(s) to be investigated?				32-33
3.3 Does the protocol describe the measure(s) of effect? (e.g. relative risk, odds ratio, deaths per 1000 person-years, absolute risk, excess risk, incidence rate ratio, hazard ratio, number needed to harm (NNH) per year)				

Comments:

Section 4: Source and study populations	Yes	No	N/A	Page Number(s)
4.1 Is the source population described?				18
4.2 Is the planned study population defined in terms of:				
4.2.1 Study time period?				19
4.2.2 Age and sex?				19
4.2.3 Country of origin?				19
4.2.4 Disease/indication?				16-17
4.2.5 Co-morbidity?				22
4.2.6 Seasonality?				
4.3 Does the protocol define how the study population will be sampled from the source population? (e.g. event or inclusion/exclusion criteria)				20-21

Comments:

Section 5: Exposure definition and measurement	Yes	No	N/A	Page Number(s)
5.1 Does the protocol describe how exposure is defined and measured? (e.g. operational details for defining and categorising exposure)				19
5.2 Does the protocol discuss the validity of exposure measurement? (e.g. precision, accuracy, prospective ascertainment, exposure information recorded before the outcome occurred, use of validation sub-study)				19
5.3 Is exposure classified according to time windows? (adapted as per this study design)				22

Section 5: Exposure definition and measurement	Yes	No	N/A	Page Number(s)
5.4 Is exposure classified based on biological mechanism of action and taking into account the pharmacokinetics and pharmacodynamics of the drug?				
5.5 Does the protocol specify whether a dose-dependent or duration-dependent response is measured?				

Comments:

Section 6: Endpoint definition and measurement	Yes	No	N/A	Page Number(s)
6.1 Does the protocol describe how the endpoints are defined and measured?				26, 33-34
6.2 Does the protocol discuss the validity of endpoint measurement? (e.g. precision, accuracy, sensitivity, specificity, positive predictive value, prospective or retrospective ascertainment, use of validation sub-study)				19-20

Comments:

Section 7: Confounders and effect modifiers	Yes	No	N/A	Page Number(s)
7.1 Does the protocol address known confounders? (e.g. collection of data on known confounders, methods of controlling for known confounders)				
7.2 Does the protocol address known effect modifiers? (e.g. collection of data on known effect modifiers, anticipated direction of effect)				

Comments:

Section 8: Data sources	Yes	No	N/A	Page Number(s)
8.1 Does the protocol describe the data source(s) used in the study for the ascertainment of:				
8.1.1 Exposure? (E.g. pharmacy dispensing, general practice prescribing, claims data, self-report, face-to-face interview, etc.)				25
8.1.2 Endpoints? (E.g. clinical records, laboratory markers or values, claims data, self-report, patient interview including scales and questionnaires, vital statistics, etc.)				32-33
8.1.3 Covariates?				24-25
8.2 Does the protocol describe the information available from the data source(s) on:				
8.2.1 Exposure? (e.g. date of dispensing, drug quantity, dose, number of days of supply prescription, daily dosage, prescriber)				25
8.2.2 Endpoints? (e.g. date of occurrence, multiple event, severity measures related to event)				25, 42-43
8.2.3 Covariates? (E.g. age, sex, clinical and drug use history, co-morbidity, co-medication, life style, etc.)				24-25
8.3 Is a coding system described for:				
8.3.1 Diseases? (e.g. International Classification of Diseases (ICD)-10)				
8.3.2 Endpoints? (e.g. Medical Dictionary for Regulatory Activities (MedDRA) for adverse events)				36
8.3.3 Exposure? (e.g. WHO Drug Dictionary, Anatomical Therapeutic Chemical (ATC)Classification System)				
8.4 Is the linkage method between data sources described? (e.g. based on a unique identifier or other)				

Comments:

--

Section 9: Study size and power	Yes	No	N/A	Page Number(s)
9.1 Is sample size and/or statistical power calculated?				35

Comments:

--

Section 10: Analysis plan	Yes	No	N/A	Page Number(s)
10.1 Does the plan include measurement of excess risks?				
10.2 Is the choice of statistical techniques described?				36-37
10.3 Are descriptive analyses included?				36-37
10.4 Are stratified analyses included?				
10.5 Does the plan describe methods for adjusting for confounding?				
10.6 Does the plan describe methods addressing effect modification?				

Comments:

--

Section 11: Data management and quality control	Yes	No	N/A	Page Number(s)
11.1 Is information provided on the management of missing data?				36
11.2 Does the protocol provide information on data storage? (e.g. software and IT environment, database maintenance and anti-fraud protection, archiving)				36
11.3 Are methods of quality assurance described?				36
11.4 Does the protocol describe possible quality issues related to the data source(s)?				39-40
11.5 Is there a system in place for independent review of study results?				

Comments:

Section 12: Limitations	Yes	No	N/A	Page Number(s)
12.1 Does the protocol discuss:  12.1.1 Selection biases?  12.1.2 Information biases? (e.g. anticipated direction and magnitude of such biases, validation sub-study, use of validation and external data, analytical methods)				39-40
12.2 Does the protocol discuss study feasibility? (e.g. sample size, anticipated exposure, duration of follow-up in a cohort study, patient recruitment)				20
12.3 Does the protocol address other limitations?				39-40

Comments:

## CONFIDENTIAL

207350 (EPI-HPV-070 VS CN PMS)

Protocol Amendment 1 Final

Section 13: Ethical issues	Yes	No	N/A	Page Number(s)
13.1 Have requirements of Ethics Committee/Institutional Review Board approval been described?				40-41
13.2 Has any outcome of an ethical review procedure been addressed?				40-41
13.3 Have data protection requirements been described?				39

Comments:

Section 14: Amendments and deviations	Yes	No	N/A	Page Number(s)
14.1 Does the protocol include a section to document future amendments and deviations?				14

Comments:

Section 15: Plans for communication of study results	Yes	No	N/A	Page Number(s)
15.1 Are plans described for communicating study results (e.g. to regulatory authorities)?				37, 48-49
15.2 Are plans described for disseminating study results externally, including publication?				48-49

Comments:

10.1.3.2.	Duration of events	16
10.1.3.3.	Distinction of adverse events in mother and infant cases	16
10.1.4.	Display of decimals.....	17
10.1.4.1.	Percentages	17
10.1.4.2.	Demographic/baseline characteristics statistics.....	17
10.1.5.	Statistical methodology.....	17
10.1.5.1.	Exact confidence intervals around proportions	17
10.2.	TFL TOC.....	18
11.	REFERENCES.....	18

CONFIDENTIAL207350 (EPI-HPV-070 VS CN PMS)
Statistical Analysis Plan**LIST OF ABBREVIATIONS**

AE	Adverse event
AEFI	Adverse Events Following Immunization
CI	Confidence Interval
eCRF	Electronic Case Report Form
ES	Exposed Set
GSK	GlaxoSmithKline
LL	Lower Limit of the confidence interval
MedDRA	Medical Dictionary for Regulatory Activities
NA	Not Applicable
PD	Protocol Deviation
PDMP	Protocol Deviation Management Plan
PI	Prescribing Information
pIMD	Potential Immune Mediated Disease
PO	Pregnancy Outcomes
SAE	Serious adverse event
SAP	Statistical Analysis Plan
SD	Standard Deviation
SDTM	Study Data Tabulation Model
SR	Study Report
TFL	Tables Figures and Listings
TOC	Table of Content
UL	Upper Limit of the confidence interval

CONFIDENTIAL

207350 (EPI-HPV-070 VS CN PMS)

Statistical Analysis Plan

1. DOCUMENT HISTORY

Date	Description	Protocol Version
04NOV2020	first version	Amendment 1: 27 JUNE 2018

CONFIDENTIAL207350 (EPI-HPV-070 VS CN PMS)
Statistical Analysis Plan

2. OBJECTIVES/ENDPOINTS

The aim of this post marketing surveillance study is to assess the safety of *Cervarix* among healthy female Chinese subjects aged between 9 and 45 years, who were vaccinated on a voluntary basis as per standard practice.

2.1. Objectives

2.1.1. Primary objective

- To assess the safety of *Cervarix* in terms of medically attended AEFIs occurring within 30 days (Day 1-30) following each immunisation, in all enrolled subjects.

2.1.2. Secondary objectives

- To assess the safety of *Cervarix* in terms of serious AEFIs occurring during the period starting at the first immunisation and ending either 12 months following the third immunisation or 24 months following the first immunisation with *Cervarix* (whichever occurs first), in all enrolled subjects.
- To assess the safety of *Cervarix* in terms of pIMDs detected during the period starting at the first immunisation and ending either 12 months following the third immunisation or 24 months following the first immunisation with *Cervarix* (whichever occurs first), in all enrolled subjects.
- To assess the safety of *Cervarix* in terms of PO when administered inadvertently within 60 days before pregnancy onset or any time during pregnancy.
- To assess the safety of *Cervarix* in terms of congenital anomalies when administered inadvertently within 60 days before pregnancy onset or any time during pregnancy.

2.2. Endpoints

2.2.1. Primary endpoint

- Occurrence, intensity and causal relationship to vaccination, of medically attended AEFIs reported during the 30-day period (Day 1-30) following each immunisation with *Cervarix*.

[figure not shown]
2.2.2. Secondary endpoints

- Occurrence, intensity and causal relationship to vaccination of serious AEFI reported during the period starting at the first immunisation and ending either 12 months following the third immunisation or 24 months following the first immunisation with *Cervarix* (whichever occurs first), in all enrolled subjects.
- Occurrence, intensity and causal relationship of pIMDs detected during the period starting at the first immunisation and ending either 12 months following the third immunisation or 24 months following the first immunisation with *Cervarix* (whichever occurs first), in all enrolled subjects.

CONFIDENTIAL207350 (EPI-HPV-070 VS CN PMS)
Statistical Analysis Plan

- Occurrence of PO when *Cervarix* is administered inadvertently within 60 days before pregnancy onset or any time during pregnancy.
- Occurrence of any congenital anomalies when *Cervarix* is administered inadvertently within 60 days before pregnancy onset or any time during pregnancy.

3. STUDY DESIGN

N= Number of subjects planned to be enrolled

AEFI: Adverse Event Following Immunisation

* Three doses of the vaccine administered intramuscularly according to the Prescribing Information (PI) for China

** Data pertaining to medically attended AEFIs, PO and pIMDs will be collected through

- patient interview and observation at immunisation visits (events that have occurred since the previous visits or that occur during or just after the visit),
- structured telephonic FU
- direct reporting by the subjects/subjects parent(s)/LAR(S)
- reporting by physician not part of this study: A physician can report a suspected AEFI by contacting the study investigator or his/her delegate).

FU: Follow-up

^ Call 1 will occur 31-45 days post second immunisation (if second immunisation was done according to PI schedule within 2.5 months post first immunisation) or 2.5 months post first immunisation if second immunisation was not done by Month 2.5.

^^ Call 1' will be scheduled 31-45 days post second immunisation in case the second immunisation occurs more than 2.5 months following the first immunisation

^^^ Call 2 will occur 31-45 days following the third immunisation

^^^^ Call 2' will be scheduled 31-45 days post third immunisation in case the third immunisation occurs more than 12 months following the first immunisation.

^^^^^ Call 3 will occur either 12 months following the third immunisation or 24 months following the first immunisation with *Cervarix* (whichever occurs first)

- Type of design: A prospective, descriptive, self-contained, multi-centre cohort study.
- This is a Targeted Safety Study (TSS) and a Post-Authorisation Safety Study (PASS).

CONFIDENTIAL207350 (EPI-HPV-070 VS CN PMS)
Statistical Analysis Plan

- Study population: The study will involve approximately 3000 female Chinese subjects aged between 9 and **45** years of age, vaccinated voluntarily as per standard practice.
- *Cervarix* will be administered as per standard practice according to the PI for China (please refer to sections on dosage and administration, instructions for administration, contraindications, warning and precautions, pregnancy, nursing mothers, drug interactions in the PI) [*Cervarix Product Information*, 2018].
- Vaccination schedule: Chinese female subjects aged between 9 and 45 years, who consented to participate in the study, are expected to receive three doses of *Cervarix* at 0, 1 and 6 months. The second dose can be administered between 1 month and 2.5 months after the first dose and the third dose between 5 and 12 months after the first dose. The vaccine will be administered intra-muscularly, in the deltoid region of the upper arm.

Note: Cervarix will be available for purchase at immunisation centres or Point of Vaccination (POV).

- Data collection: electronic Case Report form (eCRF) will be used to collect data.
- Study duration: The follow-up will be performed from enrolment until either 12 months following the third immunisation or 24 months following the first immunisation with *Cervarix* (whichever occurs first). This represents an individual subjects' total follow-up time between 18 and 24 months for subjects completing the immunisation course (3 doses) as per *Cervarix* PI schedule. Subjects who report exposure to *Cervarix* during pregnancy or pregnancy onset up to 60 days following the last immunisation will be followed-up till end of pregnancy, to observe the PO and for any possible congenital anomalies diagnosed during the first 12 months of the child's life. Thus, in such cases, an extended follow-up beyond 24 months may occur.
- Epoch 001: Prospective data collection (for each subject) starting at Visit 1 (Day 1) and ending either 12 months following the third immunisation or 24 months following the first immunisation with *Cervarix*, whichever occurs first.

The study cohorts and epoch foreseen in the study are presented in [Table 1](#).

Table 1 Study groups and epochs foreseen in the study

Study Group	Number of subjects	Age (Min/Max)	Epochs
			Epoch 001
HPV group	3000	09 years - 45 years	x

The following group names will be used in the TFLs, to be in line with the T-domains:

Group order in tables	Group label in tables	Group definition for footnote
1	HPV	Subjects who have received Cervarix

CONFIDENTIAL207350 (EPI-HPV-070 VS CN PMS)
Statistical Analysis Plan

4. ANALYSIS SETS

4.1. Exposed Set (ES)

The exposed set (ES) will include all subjects exposed to at least one dose of *Cervarix*.

4.2. Criteria for eliminating data from Analysis Sets

Elimination codes are used to identify subjects to be eliminated from analysis. Detail is provided below.

4.2.1. Elimination from Exposed Set (ES)

Code 900 (invalid informed consent or fraudulent data) and code 1030 (No administration of any dose of *Cervarix*) will be used for identifying subjects eliminated from ES

5. STATISTICAL ANALYSES

That standard data derivation rules and stat methods are described in section 10. All analyses will be performed on the exposed set.

5.1. Demography

5.1.1. Analysis of demographics/baseline characteristics planned in the protocol

Number of subjects vaccinated, completed and withdrawn with reason for withdrawal will be tabulated.

The mean age (plus range and standard deviation) and race will be tabulated.

The vaccination history, the percentage of subjects who received any vaccination within 12 months preceding Visit 1 will also be presented.

The distribution of subjects vaccinated in different centres will be tabulated.

5.1.2. Additional considerations

Demographic characteristics of subjects will be described using percentages for categorical variables and mean (standard deviation) or median (min-max) for continuous variables. The same variables will be presented descriptively, overall and by age group; 9-15, 16-17, 18-25, 26-45, ≥ 46 years old.

The percentage of subjects who had any pre-existing conditions, signs or symptoms that have started before first vaccination (general medical history) will be tabulated overall. The tabulation will be done using the MedDRA classification of System Organ Class.

CONFIDENTIAL207350 (EPI-HPV-070 VS CN PMS)
Statistical Analysis Plan**5.2. Important protocol deviations**

Code	Condition under which the code is used
900	Invalid informed consent or fraudulent data
1030	No administration of any dose of Cervarix .

5.2.1. Additional considerations

Table and listing of summaries of important protocol deviations not leading to elimination from any analyses will be generated based on the PD sheet. Table will be generated only if at least 1% of subjects from the exposed set reporting important PDs in the PD sheet.

Below are the PDs identified important, not leading to elimination in this study as per the PDMP.

Deviation Category	Sub-category
Eligibility Criteria Not Met	Related to other criteria
Eligibility Criteria Not Met	Related to vaccination
Failure to report safety events per protocol	SAE
Failure to report safety events per protocol	AEs of special interest
Failure to report safety events per protocol	Pregnancy
Failure to report safety events per protocol	Failure to confirm causality assessment
Failure to report safety events per protocol	Other

5.3. Exposure**5.3.1. Analysis of exposure planned in the protocol**

Not applicable

5.3.2. Additional considerations

The percentage of subjects who have been administered with the study vaccine will be tabulated overall. In addition, the percentage of subjects will be summarized, based on each vaccine dosage received. For example, the percentage of subjects who received only one dose, two doses and/or three doses of *Cervarix*

The percentage of subjects, who were administered any vaccine(s) other than the study vaccine (concomitant vaccination), during the period starting at the first immunisation and ending either 12 months following the third immunisation or 24 months following the first immunisation with *Cervarix* (whichever occurs first), will be reported and documented as per protocol.

CONFIDENTIAL207350 (EPI-HPV-070 VS CN PMS)
Statistical Analysis Plan

The percentage of subjects, who have used any concomitant medications, will also be tabulated.

5.4. Analysis of safety and reactogenicity**5.4.1. Analysis for Primary endpoint**

The analysis will be based on the ES.

The percentage of subjects with at least one medically attended AEFI occurring within the 30-day (Day 1-30) follow-up period will be tabulated with exact 95% CI after each vaccine dose and overall. The tabulation will be done using the MedDRA classification of System Organ Class and Preferred term.

The same tabulation will be performed for medically attended AEFI causally related to vaccination occurring within the 30-day (Day 1-30) follow-up period.

5.4.2. Analysis for Secondary endpoints

The analysis will be based on the ES.

The occurrence of serious AEFIs will be assessed throughout the entire follow-up period. Serious AEFIs will be further evaluated for their clinical relevance and relationship to vaccination.

The percentage of subjects with serious AEFI occurring within the 30-day (Day 1-30) follow-up period will be tabulated with exact 95% CI after any dose.

The occurrence of pIMD(s) will be collected and summarized through the entire follow-up period in all exposed subjects.

The PO and congenital anomalies will be summarized when *Cervarix* is administered within 60 days before pregnancy onset or any time during pregnancy. In addition, the PO will be summarized by the time of the vaccination, such as vaccination before the pregnancy, vaccination during the first trimester (LMP through week 13) of the pregnancy, vaccination during the second trimester (week 14 through week 27) of the pregnancy, vaccination during the third trimester (week 28 through term) of the pregnancy.

All secondary endpoints (serious AEFIs, pIMDs and POs) will be summarized by percentage of subjects reporting the endpoint with exact 95% CI.

CONFIDENTIAL207350 (EPI-HPV-070 VS CN PMS)
Statistical Analysis Plan**5.4.3. Additional considerations**

The percentage of subjects with at least one medically attended non-serious AEFI occurring within the 30-day (Day 1-30) follow-up period will be tabulated with exact 95% CI after any dose.

The percentage of subjects, who have used any medications, that was required to be reported as per protocol, during the whole study period will be tabulated. Medications will be coded using the GSKDRUG dictionary.

All primary and secondary endpoints (medically attended AEFIs, serious AEFIs, , casually related AEFIs , grade 3 AEFIs, pIMDs and POs) will be summarized by percentage of subjects and percentage of doses reporting the symptoms with exact 95% CI.

Incidence and nature of reported AEFIs following each dose and overall will be presented. The analysis will be done for any AEFI, medically attended AEFI within 30 days follow-up period and serious AEFI.

Adverse events will be coded using medical dictionary for regulatory activities - MedDRA classification of System Organ Class and Preferred term.

Serious AEFIs will be summarised with the rationale for identification, intensity and the outcome. The similar summary will be presented for the serious AEFIs causally related to the vaccination.

Summary of infant information (infant sex, length, weight, Apgar score) will be tabulated.

Listings of serious AEFIs, pIMDs, concomitant vaccination(for the subjects with at least one medically attended AEFI causally related to the vaccine), pregnancies and infants (with / without congenital anomalies) will be generated.

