## 7. RATIONALE AND BACKGROUND

*Cervarix* is a prophylactic HPV (Human papillomavirus) vaccine developed by GlaxoSmithKline (GSK) Biologicals. It is based on the L1 proteins of HPV-16 and HPV-18 formulated with AS04 (comprising of aluminium hydroxide [Al (OH)3] and 3-*O*-desacyl-4'-monophosphoryl lipid A [MPL]), indicated for women aged 9 to 45 years of age in China.

The safety profile of *Cervarix* vaccine has been characterised during clinical development and during the post marketing phase. Characterisation of *Cervarix* safety profile during the post marketing phase was achieved through passive reporting systems for adverse events following immunisation (AEFI) and the conduct of several post marketing studies [[Angelo, 2014](#); [Stillo, 2015](#)].

The post marketing data is similar to the pre-licensure data with respect to the most commonly reported adverse reactions such as injection site reactions, headache, myalgia, pyrexia and gastrointestinal symptoms. Also, additional adverse reactions of unknown frequency such as lymphadenopathy, allergic reactions, angioedema have been identified during the post marketing experience and listed in the summary of product characteristics (SmPC) [[Cervarix Summary of Product Characteristics, 2016](#)].

Adverse events (AE) of interest identified during pre-licensure clinical development are monitored. For *Cervarix*, these AE of interest include the new onset and exacerbation of potential immune-mediated diseases (pIMDs) after vaccination, and pregnancy outcomes (PO) associated with unintended vaccine exposure during pregnancy [[Lopez-Fraqued, 2017](#)].

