### 9.1.1.      Discussion of study design

This prospective, surveillance study will collect data regarding the safety of *Cervarix* vaccine. The study will be conducted in Chinese population receiving the vaccine voluntarily as per standard practice, complementing the safety and reactogenicity data collected in the clinical trial HPV-039 [[Zhu](#), 2014].

The study will actively collect data on a large range of AEFIs, complementing passive routine pharmacovigilance from the China Adverse Drug Reaction Monitoring System (CADRMS) [Zhang, 2014].

The present study considers a follow-up of 12 months following the third immunisation with *Cervarix*, as it represents a reasonable maximum theoretical risk interval for new onset of pIMDs [Tavares, 2013].

The study is descriptive in nature, without any hypothesis testing. The conduct of a hypothesis testing study analysing the risk of a specific AEFI by comparing vaccine exposed subjects to non-exposed subjects would require electronic data collection system. This system should enable the linkage at the individual level of AEFI with the immunisation status. While such linked databases exist in some countries (for example in the UK with CPRD GOLD), they are not yet available in China. A prospective cohort design was seen as the only feasible design, given that healthcare databases which allow analysis of epidemiological association between specific AEFIs and vaccination are not available in China [Liu, 2015].

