**9.3. Variables****9.3.1. Safety definitions****9.3.1.1. Adverse event following immunisation (AEFI)**

Any untoward medical occurrence in a subject which follows immunisation, whether or not considered related to the vaccine.

An adverse event following immunisation (AEFI) can therefore be any unfavourable and unintended sign (including an abnormal laboratory finding), symptom, or disease (new or exacerbated) temporally associated with the use of a vaccine. For marketed medicinal products, this also includes failure to produce expected benefits (i.e., lack of efficacy), abuse or misuse.

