### 9.3.1.4. Potential immune mediated disease (pIMD)

Potential immune mediated diseases (pIMDs) are a subset of AEFIs that include autoimmune diseases and other inflammatory and/or neurologic disorders of interest which may or may not have an autoimmune aetiology. A list is provided in [Table 3](#).

Table 3 List of pIMDs

Neuroinflammatory disorders	Musculoskeletal disorders	Skin disorders

 
• Cranial nerve neuropathy, including paralysis and paresis (e.g. Bell's palsy).
 
• Optic neuritis.
 
• Multiple sclerosis.
 
• Transverse myelitis.
 
• Guillain-Barré syndrome, including Miller Fisher syndrome and other variants.
 
• Acute disseminated encephalomyelitis, including site specific variants e.g.: non-infectious encephalitis, encephalomyelitis, myelitis, myeloradiculoneuritis.
 
• Myasthenia gravis, including Lambert-Eaton myasthenic syndrome.
 
• Demyelinating peripheral neuropathies including:
 
• Chronic inflammatory demyelinating polyneuropathy,
 
• Multifocal motor neuropathy
 
• Polyneuropathies associated with monoclonal gammopathy.
 
• Narcolepsy.
 
	
 
• Systemic lupus erythematosus and associated conditions
 
• Systemic scleroderma (Systemic sclerosis), including:
 
• Diffuse Scleroderma
 
• CREST syndrome
 
• Idiopathic inflammatory myopathies, including:
 
• Dermatomyositis
 
• Polymyositis
 
• Anti-synthetase syndrome.
 
• Rheumatoid Arthritis and associated conditions including:
 
• Juvenile Idiopathic Arthritis
 
• Still's disease.
 
• Polymyalgia rheumatica.
 
• Spondyloarthropathies, including:
 
• Ankylosing Spondylitis,
 
• Reactive Arthritis (Reiter's Syndrome),
 
• Undifferentiated Spondyloarthritis,
 
• Psoriatic Arthritis,
 
• Enteropathic arthritis.
 
• Relapsing Polychondritis.
 
• Mixed Connective Tissue disorder.
 
• Gout.
 
	
 
• Psoriasis.
 
• Vitiligo.
 
• Erythema nodosum.
 
• Autoimmune bullous skin diseases (including pemphigus, pemphigoid and dermatitis herpetiformis).
 
• Lichen planus.
 
• Sweet's syndrome.
 
• Localised Scleroderma (Morphea).
 

Vasculitis	Blood disorders	Others

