### **9.12. Limitations of the research methods**

The study population may not be representative of the entire population eligible for vaccination. This is because the administration of vaccine will not be part of the universal vaccination programme but performed on a voluntary basis as per standard practice in vaccination centres. In particular, there may be an uneven age distribution of the study participants.

The study is descriptive and is not designed to assess an epidemiological association between a given adverse event and vaccination.

The sample size of approximately 3000 subjects meets the requirements of the Chinese regulation. Due to the low incidence of pIMDs (generally < 40 per 100,000) in adolescent girls and young women and the limited number of expected exposure to *Cervarix* during pregnancy, the study will be limited for the detection of these rare events.

The study will only enroll subjects vaccinated with *Cervarix* and thus will not have a control group. Therefore, the observed frequency of AEFI will be interpreted in terms of safety data generated in clinical trials, post-licensure epidemiological studies and background incidence rates reported in the literature.

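### The single pIMD percentage in SAP 5.4.2 pools new-onset disease with flares of existing disease, so it is not comparable with external figures on a new-onset basis

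*SAP*

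**What the plan says.** **The summary.** SAP 5.4.2 states: "The occurrence of pIMD(s) will be collected and summarized through the entire follow-up period in all exposed subjects". The measure follows in the same section: "All secondary endpoints (serious AEFIs, pIMDs and POs) will be summarized by percentage of subjects reporting the endpoint with exact 95% CI". SAP 5.4.3 adds a percentage of doses. Neither section separates new onset from exacerbation.

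**What counts as an event.** Protocol section 7 says that for this vaccine "these AE of interest include the new onset and exacerbation of potential immune-mediated diseases (pIMDs) after vaccination". Protocol 9.3.1.4 adds: "Potential immune mediated diseases (pIMDs) are a subset of AEFIs that include autoimmune diseases and other inflammatory and/or neurologic disorders of interest". The parent definition of an AEFI in 9.3.1.1 covers any "symptom, or disease (new or exacerbated) temporally associated with the use of a vaccine". A flare of known disease is therefore a pIMD event.

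**Who is in the denominator.** Protocol 9.2.2 admits any Chinese female aged 9 to 45 who is vaccinated voluntarily, can comply and consents. The only exclusion listed in 9.2.3 is a child in care, with a pointer to the Prescribing Information. Section 9.2.5.2.2 asks for pre-existing immune and neurological disorders to be recorded at enrolment.

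**How the result will be read.** Protocol 9.12 notes that there is no control group. It says that AEFI frequency will be interpreted against clinical trials, post-licensure epidemiological studies and "background incidence rates reported in the literature". The follow-up of 12 months after the third dose is justified in 9.1.1 because "it represents a reasonable maximum theoretical risk interval for new onset of pIMDs".

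**The concern.** The numerator holds two kinds of event, and the outside yardsticks appear to hold one. Incidence counts new cases by its meaning, although the protocol does not spell this out. Section 7 summarises the Chinese efficacy trial in terms of new-onset autoimmune diseases. The UK database cohort described there is listed among the references under a title about newly arising autoimmune disease. The follow-up window rests on new onset as well.

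New-onset pIMDs should be very few in 3000 women, so even a handful of flares can dominate the pooled figure. A reader could then see an apparent excess of new disease where there is none, or be unable to tell what the new-onset frequency was. The regulator's approval letter, cited in protocol 7.1, asked specifically for information on immune-mediated diseases, so this table will be looked at closely.

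**Working it through.** **1. The plan's own intervals.** The documents state no expected pIMD percentage. Their exact intervals for N = 3000 (protocol Tables 4 and 5) reproduce with the Clopper-Pearson method. For example, 6/3000 = 0.20% gives 0.07% to 0.43%, and 15/3000 = 0.50% gives 0.28% to 0.82%.

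**2. New-onset cases.**
- Inputs: N = 3000 (protocol 9.5.1); follow-up of 18 to 24 months for women completing the course (protocol 9.1, SAP 3); incidence generally under 40 per 100,000 (protocol 9.12).
- Assumptions: the 40 is per year and covers all pIMDs together. The protocol states neither.
- Formula: E = N × 40/100,000 × years.
- 18 months: 3000 × 0.0004 × 1.5 = 1.8 women (0.06%).
- 24 months: 3000 × 0.0004 × 2 = 2.4 women (0.08%).

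These are ceilings, because the protocol's figure is an upper bound.

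**3. Flares.** The documents give neither the share of women entering with a listed pIMD nor the share of those who flare. I assume ranges of 0.5% to 5% and 5% to 30% during follow-up. Formula: F = 3000 × prevalence × flare share. The pooled count divided by the new-onset count is (E + F)/E.

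| Prevalence | Flare share | F | Pooled, 18 mo | Ratio, 18 mo | Pooled, 24 mo | Ratio, 24 mo |
|---|---|---|---|---|---|---|
| 0.5% | 5% | 0.75 | 2.55 | 1.4 | 3.15 | 1.3 |
| 0.5% | 10% | 1.5 | 3.3 | 1.8 | 3.9 | 1.6 |
| 1% | 10% | 3 | 4.8 | 2.7 | 5.4 | 2.3 |
| 2% | 20% | 12 | 13.8 | 7.7 | 14.4 | 6.0 |
| 5% | 30% | 45 | 46.8 | 26 | 47.4 | 20 |

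The ratio equals 1 + F/E. If the 40 per 100,000 is per disease, E for the whole of protocol Table 3 is larger and every ratio moves towards 1. If true incidence is well below the ceiling, the ratios rise.

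**4. How few events matter.** Under the reading in step 2, six pooled women (exact CI 0.07% to 0.43%) put the lower limit above 0.06%. Seven (0.09% to 0.48%) put it above 0.08%.

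**5. Whether the SAP separates the two elsewhere.** Medical history is tabulated overall by System Organ Class (5.1.2) and is not crossed with pIMD events. Section 9 has no study-specific rules. The before/after flag in 10.1.1 and 10.1.2.1 dates an event relative to a dose; it does not identify disease already present at entry. A pIMD listing is planned (5.4.3), with no onset field named.

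**6. Effect of the denominator.** Take two new-onset cases. All women: 2/3000 = 0.067%. Removing 1% with prior disease: 2/2970 = 0.067%. Removing 5%: 2/2850 = 0.070%. The numerator is what matters.

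**The case against.** The strongest reply is that nothing is decided on this figure. The analyses are descriptive (SAP 6), and protocol 9.12 says that the study is not designed to assess association. Each pIMD receives an investigator's causality assessment that considers underlying disease and medical history (protocol 11.1.2.2). Safety physicians review the cases continuously (11.3), and all will be listed. With perhaps five cases, a reader could sort them by hand. The table layouts are in a separate document not available here and might contain a split. The stated aim also concerns healthy women, and the Prescribing Information, likewise not available here, may restrict entry.

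Much of this stands. It lowers the chance that flares are silently taken for new disease, and the number of women entering with a pIMD is unknown. It does not change the reported percentage, and sorting cases by hand once they are known is weaker than a rule set beforehand. The contraindication check in protocol 9.2.5.2.4 gives hypersensitivity as its example and asks about pregnancy; it does not mention immune disease.

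A reader might infer that the plan sets the pIMD percentage directly against 40 per 100,000. It does not. That figure appears in a paragraph on the limited ability to detect rare events. The sentence on interpretation comes in the next paragraph, concerns AEFIs in general, gives no number and names three kinds of source. The figure also refers to adolescent girls and young women, whereas the study enrols up to age 45.

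**Conclusion.** The point holds as a problem of comparability. The pIMD percentage mixes new onset with exacerbation in a population not restricted to women free of such disease, while the described external sources and the follow-up rationale are on a new-onset basis.

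The size cannot be fixed from the documents. The 1.8 to 2.4 new-onset cases are a ceiling that depends on reading the 40 per 100,000 as annual and for all pIMDs. The ratio of about 1.4 to 26 at 18 months (1.3 to 20 at 24 months) also depends on the assumed prevalence and flare ranges. It would be a step too far to say that flares will more than double the count: some combinations in the range do not reach that, and a per-disease reading shrinks all of them.

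Nor would a split alone make the result an incidence rate. A percentage accumulated over 18 to 24 months is on a different scale from a rate per person-time.

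**What to change.** In SAP 5.4.2, add a rule that classifies each pIMD as new onset or exacerbation from the medical history recorded at Visit 1, with a category for cases that cannot be classified. Tabulate new onset and exacerbation separately with exact 95% CIs, keeping the pooled figure if wanted, and show the class in the pIMD listing. For comparison with external incidence, use only the new-onset figure and also express it per person-time. When the 40 per 100,000 is cited in the report, give its time unit and say whether it is per disease or overall.

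Removing women with the condition at baseline from the denominator is optional, since it barely changes the figure and would need a separate denominator for each disease.

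The cost is a short derivation rule, a split table and a person-time calculation from dates already held. No new data or subjects are needed. Because history is self-reported at interview, some events will be misclassified, and the report should say so.
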